[name]

University of Wyoming
[name]
Co-Investigator
[name]
[name]
[name]
[contact]
Email: [contact]

PRÉCIS

Study Title

A Proof of Concept and Feasibility Trial of Compassion Meditation for PTSD

Objectives

1. To refine an existing compassion meditation protocol for PTSD by evaluating participants' reactions to the intervention components and refining the practices to maximize engagement and induction of cognitive/emotional states that are most likely to counteract PTSD.
2. To evaluate the acceptability of and refine a likely future control condition (i.e., relaxation).
3. To identify the best strategies by which to recruit and retain subjects (including women) in the protocol.
4. To evaluate the feasibility of conducting compassion meditation as an intervention for PTSD.
5. To establish preliminary estimates of effect size and other parameters to inform future efficacy studies of compassion meditation.
6. To identify potential mechanisms of action and predictors of response.

Design and Outcomes

This project is a feasibility and proof of concept study of compassion meditation (CM) for Veterans with posttraumatic stress disorder (PTSD; $N \approx 100$). Phase 1 (N ≈ 60, nonrandomized, Protocol Refinement), will consist of up to 4 CM and 2 Relaxation groups with 6-12 participants in each group. Iterative refinement of the treatment protocols will be done based on quantitative and qualitative data from participants. Phase 2 (N ≈ 40), Pilot Evaluation is a randomized controlled study with 4 groups (2 CM and 2 relaxation groups, 6-12 in each group) to examine the feasibility of a randomized trial and to estimate response to CM.

Interventions and Duration

The interventions to be compared are CM and Relaxation Training.

- CM is a meditative practice focused on the wish that others and the self may be free of suffering. The Compassion Meditation Protocol was developed by consultant Geshe [name]. It consists of 8 2-hour sessions and accompanying at home practice. The intervention begins with basic breathing-focused meditation and awareness of internal experience. Participants go on to cultivate compassion toward the self and others.
- The Relaxation Training Protocol utilized herein was used in Taylor et al.'s (2003) PTSD trial. It will be delivered in 8 2-hour sessions with accompanying at home practice. Participants will be taught a variety of relaxation techniques and how to apply these to enhance coping with daily stressors and symptoms.

Participant participation will be approximately 3 months. Baseline evaluation will be completed within 1 month of the beginning of the treatment groups. Groups will last 8 weeks, and post-treatment assessment will be completed at the end of the groups.

Sample Size and Population

Participants in both phases will be Veterans with PTSD who are able to consent and willing to participate (refer to Human Subjects for detailed inclusion/exclusion criteria). In Phase 1, we will run up to 4 CM groups and 2 relaxation groups; we will aim for a group size of 6-12 in each group. In Phase 2, we will conduct a pilot study with random assignment to 4 groups (2 CM and 2 relaxation groups, 6-12 in each group. We estimate that 60 people will take part in Phase 1 of the research, and approximately 40 participants in Phase 2, for a total sample size of approximately 100 people.

1. STUDY OBJECTIVES

1.1 Primary Objective

1. To refine an existing compassion meditation protocol for PTSD by evaluating participants' reactions to the intervention components and refining the practices to maximize engagement and induction of cognitive/emotional states that are most likely to counteract PTSD.
2. To evaluate the acceptability of and refine a likely future control condition (i.e., relaxation).
3. To evaluate the feasibility of conducting compassion meditation as an intervention for PTSD.
4. To establish preliminary estimates of effect size and other parameters to inform future efficacy studies of compassion meditation.

1.2 Secondary Objectives

1. To identify the best strategies by which to recruit and retain subjects (including women) in the protocol.
2. To identify potential mechanisms of action and predictors of response.

2. BACKGROUND AND RATIONALE

2.1 Background on Condition, Disease, or Other Primary Study Focus

PTSD is a psychopathological response to exposure to a traumatic stressor and is characterized by recurrent re-experiencing of the event, avoidance of reminders of the trauma, negative alterations in mood and cognitions, and increased arousal (American Psychiatric Association, 2014). The disorder typically follows a chronic course and leads to significant work and social impairment and increased healthcare utilization (e.g., Hidalgo & Davidson, 2000; Jaycox & Foa, 1999; Stein, McQuaid, Pedrelli, Lenox & McCahill, 2000). Although there are psychotherapies that effectively reduce PTSD symptoms, additional approaches are needed because no single intervention is universally effective, acceptable and/or feasible (Bradley, Greene, Russ, Dutra, & Westen, 2005; Schottenbauer, Glass, Arnkoff, Tendick & Gray, 2008).

There is a strong demand by patients and clinicians for complementary and alternative treatments such as meditation for the amelioration of symptoms of posttraumatic stress disorder (PTSD). Mental health problems are among the most frequently cited reasons for seeking help from a complementary and alternative medicine provider (Strauss, Coeytaux, McDuffie, Nagi, & Williams, 2011) and a recent national survey shows that 40% of patients with PTSD used a

complementary and alternative medicine approach in the past year, with meditation being one of the most commonly used approaches (Libby, Pilver, & Desai, 2012). In spite of this, there is little empirical evidence to support their use. Compassion meditation, which is a meditative practice that focuses on the wish that the self and others be free of suffering, has been associated with positive changes in nonclinical samples. In particular, compassion meditation has been shown to increase positive emotion and social connectedness, both of which are areas of deficit for individuals with PTSD. However, CM has never been evaluated in relation to PTSD.

2.2 Study Rationale

A variety of meditation techniques are currently being used to address mental and physical health issues, and several studies show that meditation is acceptable to Veterans with PTSD (Bormann et al., 2011; Kearney et al., 2012; Niles et al., 2012). It may be unwise, however, to view all meditative practices as interchangeable. For example, baseline brain activation appears to predict the type of meditation (mindfulness or compassion meditation) in which an individual will engage (Mascaro, Rilling, Negi, & Raison, 2013b).

We hypothesize that CM will relieve PTSD symptoms and improve quality of life by fostering positive emotion and social connectedness, processes that are negatively impacted by PTSD. Evidence for this hypothesis comes from observed responses to CM and loving kindness meditation (LKM), a closely related approach. Hutcherson, Seppala and Gross (2008) compared a 7-minute LKM exercise to an imagery exercise and found that even this very brief intervention, as compared to imagery, led to increased positive mood and decreased negative mood. Beneficial effects are also observed when LKM is delivered over multiple sessions as an intervention. LKM delivered in six 60-minute sessions over 7 weeks to workers ($n = 102$), led to increased positive emotion as compared to WL control ($n = 100$) (Fredrickson, Cohn, Coffey, Pek, & Finkel, 2008). Results from a small pilot study ($n = 18$) of LKM for negative symptoms of schizophrenia showed that the practice increased positive emotion and decreased negative emotion (Garland et al. 2010) and indicates that this technique can induce positive emotion in clinical samples. Evidence from functional MRI shows activation in areas typically associated with positive affect (left medial prefrontal cortex and anterior cingulate gyrus) in an expert meditator engaged in CM (Engstrom & Söderfeldt, 2010). Positive emotions are thought to enhance coping (Fredrickson, 2001) and have been associated with resilience, i.e., the ability to recover from negative experiences and to change based on situational demands (Tugade & Fredrickson, 2004). In particular, positive emotions have been tied to the process of coping with highly stressful events. For example, Fredrickson and colleagues (2003) found that positive emotions were a critical component in resilience among college students after the September 11 terrorist attacks. Similarly, bereaved caregivers who experienced positive emotion during their grief found more positive meaning in their loss and demonstrated more long-term goal-setting and planning, which corresponded to greater well being 12 months later (Moskowitz, 2001). CM is also thought to enhance social connectedness. LKM has been associated with more positive explicit and implicit reactions to others (Hutcherson et al., 2008), and CM is linked to increased empathic accuracy and activation of associated brain circuitry (Mascaro, Rilling, Negi, & Raison, 2013a). A sense of connection, or belongingness, is associated with better psychological and social functioning (Hagerty, Williams, Coyne, & Early, 1996), including reduced anxiety and greater self-esteem (Lee & Robbins, 1998), and may have a protective effect against stress, depression and PTSD (see, for example Cacioppo, Hughes, Waite, Hawkley, & Thisted, 2006; Cacioppo & Patrick, 2008). Conversely, social isolation may be the strongest and most reliable predictor of suicidal

thoughts and behavior (Van Orden et al., 2010) and deficits in empathy have been associated with verbal aggression in veterans with PTSD (Teten, Miller, Bailey, Dunn, & Kent, 2008).

CM has not been specifically evaluated for PTSD but has been applied for stress reduction and in one clinical sample. Pace et al. (2009) recruited 61 college students into a study comparing CM and health education discussion. Participants were assessed using a standardized stress test (public speaking followed by mental arithmetic) and physiological measures. The more students practiced meditation at home, the less distress they reported after the stress test. In the single study with a psychiatric population, Johnson et al. (2011) conducted a pilot study of LKM with individuals diagnosed with schizophrenia-spectrum disorders (n = 18). Eighty-eight percent completed the treatment, and the practice was perceived to be easy, enjoyable and useful. Participants actively engaged in the meditation, practicing an average of 3.7 days per week. LKM was associated with a large effect size increase in positive emotion and life satisfaction, a large effect size reduction in negative symptoms and anhedonia, and a medium effect size reduction in asociality. These gains generally were maintained over a 3 month follow-up period (Johnson et al., 2011). Finally, Carson et al. (2005) applied LKM for low back pain. They found that, as compared to standard care, LKM led to reduced general psychological distress, anxiety and hostility after the intervention and 3 months later.

Interventions. The initial CM group for Phase I of this study will follow the existing Emory Compassion Meditation Protocol. The protocol will be iteratively refined until we have a version (and accompanying manual) that has been optimized for veterans. This final version will be used in Phase 2.

Relaxation Training was selected as the control condition. It was selected because it is a good match for nonspecific aspects of the meditative practice (e.g., attention, support, contact with a mental health provider) and it is structurally similar to meditation (e.g., restful, in session and at home exercises).

Both groups will be delivered in 8 two-hour sessions by a trained therapist.

3. STUDY DESIGN

Design. The proposed project is a feasibility and proof of concept study of compassion meditation (CM) for posttraumatic stress disorder (PTSD). Phase 1 (N ≈ 60, nonrandomized, Protocol Refinement), will consist of up to 4 CM and 2 Relaxation groups with 6-12 participants in each group. Iterative refinement of the treatment protocols will be done based on quantitative and qualitative data from participants. Phase 2 (N ≈ 40), Pilot Evaluation is a randomized controlled study with 4 groups (2 CM and 2 relaxation groups, 6-12 in each group) to examine the feasibility of a randomized trial and to estimate response to CM.

Outcomes. In Phase 1, outcomes will include treatment credibility, qualitative reactions to groups, time spent practicing, satisfaction, emotional responding, social connectedness, self-compassion and heart rate variability (HRV).

Study population and groups. Participants in both phases will be Veterans with PTSD who are able to consent and willing to participate. Co-occurring disorders such as depression, anxiety, or treated substance abuse or dependence problems are permitted provided that PTSD is the primary presenting complaint. We estimate that 60 people will take part in Phase 1 of the research and approximately 40 participants in the second phase, for a total sample size of approximately 100 people.

Study location. The study will take place at the VA San Diego Healthcare System, with groups conducted at the Oceanside Mental Health Clinic.

Duration. Phase 1 will last approximately 18 months, with 6 months of therapist training and 12 months of recruitment and delivery of the interventions. Phase 2 will last approximately 12 months. For a given participant, involvement in the study will last approximately 3 months, including assessments before and after the group and the 8-week intervention.

Interventions. The first CM group in Phase 1 will follow the existing Emory Compassion Meditation Protocol. This well-developed protocol has been used extensively with non-clinical populations but some initial refinement will be done to assure that the material is accessible to veterans. The subsequent groups will be delivered using the protocol version developed with the prior group until a well-received protocol has been established. The initial relaxation group will follow [name] protocol with minor modification to match the timeline of the CM protocol (i.e., extending sessions from 90 minutes to 2 hours and providing similar amounts of homework) and modality of administration (group rather than individual). If necessary, this protocol will be refined based on participant feedback as well. The final versions of the protocols will be employed in Phase 2. Both types of groups will be conducted in person by a trained licensed clinical psychologist in eight 2-hour sessions.

Randomization. There is no randomization in Phase 1. In Phase 2, groups will be randomized in a 1:1 allocation ratio to CM or Relaxation Training; no stratification will be used. The assessor will be kept blind to treatment condition. Random assignment of groups to study conditions will be conducted by study statistician, [name], after the groups have been formed. Prior to enrollment, the study statistician will write a program in SPSS (IBM Software Group. SPSS User' Guide, Version 21. Chicago, Il, 2013) to create a list of subject identification numbers with randomized treatment assignments (2 CM and 2 relaxation groups), which will be held by the unblended project coordinator during the trial. Variable blocked randomization will be used with random block size (4 or 6). Separate lists (up to 4) of replacement subject identification numbers will also be created so that replacement subjects are assigned the same treatment as subjects they are replacing. Subjects will be randomized to study treatment group in a 1:1 ratio.

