4.3 Study Enrollment Procedures

Potential participants will be recruited from VA mental health clinics and the community. We will interface with staff at the VA Medical Center, VA Oceanside Community Based Outpatient Clinic, and Vet Center clinics to encourage referral of interested patients to the study. Clinicians will introduce the study to their patient and if the veteran is interested will give his/her permission to pass their name and phone number to the study coordinator. We will use a tool adapted from other approved VA studies that provides a summary of the study objectives, lists patient's name and phone number and that the patient initials. This tool will be given to the study coordinator. We will also recruit from the community through posting flyers in local mental health clinics, by use of advertisements in periodicals (especially those that focus on complementary and alternative healing practices) and via Web-based resources. The coordinator will maintain a study log to document the source of all potential participants; we will match this information with data about whether or not they participated and, if not, reasons for ineligibility to subsequently analyze the effectiveness of various recruitment practices.

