This study will be conducted at the VA Medical Center in compliance with Title 45 Part 46 of the CFR pertaining to protection of human subjects. Signed consent documents for VA subjects use VA form 10-1086. Consenting will take place at the Oceanside VA clinic with a trained assessor/study coordinator in a private room and the participant will be given ample time to read the consent form and ask questions. At the first visit, prior to initiation of any study-related procedures, subjects will give their written consent to participate in the study after having been informed about the nature and purpose of the study, participation/termination conditions, risks, and potential benefits. Informed consent is a process that is initiated prior to the individual's agreeing to participate in the study and continuing throughout the individual's study participation. Upon reviewing the document, the assessor will explain the research study to the participant and answer any questions that may arise. Extensive discussion of risks and possible benefits of this therapy will be provided to the participants as needed. The investigator will explain study procedures. The participants will sign the informed consent document prior to any procedures being done specifically for the study. The participants may withdraw consent at any time throughout the course of the trial. A copy of the informed consent document will be given to the participants for their records. The rights and welfare of the participants will be protected by emphasizing to them that the quality of their medical care will not be adversely affected if

they decline to participate in this study. VA subjects will consent to the audio-video recording using VA form 10-3203.

Decisional capacity will be assessed based on the interviewer's judgment during the dialog that takes place during recruitment and screening. In addition, the participant participates in a comprehensive psychological assessment as part of the screening including questions about traumatic brain injury. We also anticipate that the clinician referral will screen out anyone with severe cognitive problems. Participants with questionable decisional capacity will be excluded from the study.

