9.2 Sample Size and Randomization

For Phase 1, we estimated sample size based on past experience in intervention development; we believe that we will need to run 4 CM groups to achieve Phase 1 refinements (e.g., [name], Norman, & [name], 2006). For the relaxation protocol, which was used in a prior PTSD study, we will begin with our modified version and expect 2 groups will be sufficient given the very minor modification. We will aim for a group size of 6-12, which can be recruited within the 1-month period we have allocated to recruitment before each group. Thus, we estimate that 60 people will take part in Phase 1 of the research.

In Phase 2, we will conduct a pilot study with 4 groups (2 CM and 2 relaxation groups, 6-12 in each group) to examine the feasibility of a randomized trial and response to CM. Thus, we anticipate approximately 40 participants in the second phase

Treatment Assignment Procedures

In phase 2, groups will be randomly assigned a treatment condition in a 1:1 ratio. The assessor will remain blind to these assignments; the study team will be careful not to disclose which group or therapist is seeing a given participant and participants will be asked to refrain from discussing the nature of their intervention during assessments. There is no need for breaking blind as treating clinicians will be aware of the treatment assignment.

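### Phase 2 allocation concealment is not assured: a pre-made list of assignments sits with an unblinded coordinator whom the protocol does not separate from recruitment and consent

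*Combined protocol and SAP*

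**What the plan says.** Section 3 (Randomization) describes Phase 2 allocation in two ways.

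- **By group, late.** "groups will be randomized in a 1:1 allocation ratio to CM or Relaxation Training; no stratification will be used", and "Random assignment of groups to study conditions will be conducted by study statistician" once the groups exist. Section 6.2.2 also places randomization after baseline, close to the start of the groups.
- **By participant, early.** Before enrollment the statistician programs a list pairing ID numbers with arms, in random blocks of 4 or 6, "which will be held by the unblended project coordinator during the trial". Up to four further lists give each replacement the arm of the person replaced. The paragraph ends: "Subjects will be randomized to study treatment group in a 1:1 ratio".

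A coordinator appears in several other places. In section 4.3 referring clinicians obtain permission from patients, who "give his/her permission to pass their name and phone number to the study coordinator", and the coordinator logs the source of all potential participants. The consent text says: "Consenting will take place at the Oceanside VA clinic with a trained assessor/study coordinator in a private room". Sections 6.2.1 and 11.2 say nearly the same.

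On blinding, section 6.2.3 keeps all Phase 2 personnel blind until data lock, except the person who executes randomizations (name removed) and the therapists. Section 9.2 states: "The assessor will remain blind to these assignments". Section 10.3.1 makes the Phase 2 assessor a doctoral-level psychologist.

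**The concern.** Concealment means that whoever brings a person into the trial cannot know the arm that person will receive. A list made before enrollment and kept by someone involved in referral, scheduling or consent removes that protection, and random block sizes do not restore it. A participant could be hurried, delayed or discouraged according to the coming arm without anyone intending harm.

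This matters even in a pilot. Phase 2 is meant to test whether a randomized trial is feasible, so its allocation procedure is part of what is being tested. Section 9.6 compares CM with Relaxation on CAPS-5, the Phase 2 primary outcome. Patients and therapists cannot be blinded (section 5.2), so concealment and the blinded rating are the main safeguards. With about 40 participants, a few selective entries could move the effect estimate that is to inform later trials.

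**Working it through.** The plan gives no figure for this point, so the main check sets the passages side by side.

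**1. Is the list holder separate from recruitment?** The term project coordinator occurs only in section 3. Elsewhere the text says study coordinator or the coordinator. No sentence says they are the same person, and none says they are different. No sealed, central or off-site release is described.

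**2. Do the two allocation procedures give the same protection?**
- Participant-level list made before enrollment: the holder can know the arm attached to each ID before that person enters.
- Whole groups assigned after formation: those enrolled are already fixed when the arm is drawn, so initial entry is protected. If the groups are formed and assigned one after another, anyone who knows the first three arms knows the fourth.
- Replacements: the arm is that of the person replaced, so it is knowable before the replacement is recruited under either procedure.

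**3. Does the blinding section account for the list holder?** Section 6.2.3 has two exceptions. Section 3 gives randomization to the statistician, so an unblinded coordinator fits neither exception by role. The name in the first exception has been removed, so the coordinator could be meant there, but that would then conflict with section 3.

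**4. How predictable is the next assignment without the list?** Assume that past assignments are known and that the guess is always the arm that is behind, with a coin toss at ties. For a block of 2m, expected correct guesses = m + (4^m / C(2m, m) − 1)/2.
- Block of 4: 2 + (16/6 − 1)/2 = 2.833, and 2.833/4 = 71%.
- Block of 6: 3 + (64/20 − 1)/2 = 4.1, and 4.1/6 = 68%.
- Equal mix of the two: (2.833 + 4.1)/(4 + 6) = 69%. A simulation of 40 participants (40,000 runs) also gives 69% (0.689).
- Two CM and two Relaxation groups assigned in sequence (6 possible orders): (1/2 + 2/3 + 2/3 + 1)/4 = 71%.

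With the participant-level list the figure is 100%. The fair comparison is therefore 100% against about 69%, not against 50%.

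**5. How large could the effect be?** This is an illustration on assumed inputs: 20 per arm (40/2), and two participants swapped between arms with two whose expected CAPS-5 differs by 1 SD. Each arm mean moves 2 × 1/20 = 0.10 SD, in opposite directions, so the difference is 0.20 SD with no treatment effect. For scale, the chance standard error of the arm difference is √(2/20) = 0.32 SD.

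**The case against.** The strongest reply is that the plan already has the right ingredients: the statistician assigns groups after they are formed, and randomization follows baseline. If only that procedure is followed, no one can be steered at initial entry. This stands, and it is why a reader who infers that concealment fails, or that the problem is the same whichever unit is randomized, goes too far. It does not dispose of the point, because the same paragraph also creates an earlier list and hands it over, and replacements are not covered.

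A reader might also infer that one person both recruits and holds the list. The documents do not say so; the unblinded label could equally mark a separate role. Nor do they give the coordinator the discretionary entry decisions: capacity is judged by the interviewer, expected medication change is the provider's view, and MINI, MoCA and DES support the rest.

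A third tempting reading is that the CAPS-5 rater is unblinded, because consent is taken by an 'assessor/study coordinator'. The slash may simply mean either one, and the consent text covers both phases. Sections 3 and 9.2 require a blind assessor, and section 3 calls the list holder unblinded, so one person could not hold both roles without breaching the protocol.

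Finally, the 0.20 SD rests on chosen inputs and is smaller than the chance standard error. The baseline-adjusted regression that section 9.6 allows would reduce an imbalance visible at baseline, and the trial is a pilot whose analyses are declared preliminary. All of that limits the weight of the figure. It is no reason to leave the allocation procedure ambiguous.

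**Conclusion.** The point holds in a limited form and should be corrected before Phase 2. Concealment is not assured, for three reasons: the list holder is not separated from the coordinator who recruits and is named in consent; section 3 contradicts itself on the unit and timing of assignment; and replacements' arms can be known in advance. Section 6.2.3 also conflicts with section 3 on who is unblinded. Exposure of the CAPS-5 rating is possible only through the loose consent label and is not established.

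The size is conditional. If the participant-level list is the working procedure, its holder knows 100% of listed assignments against about 69% guessable without it. If groups are assigned only after all of them are formed, the exposure shrinks to replacements. The 0.20 SD shows what two selective swaps could do and is not an estimate of bias in this trial.

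**What to change.** - **Section 3:** settle whether groups or participants are randomized. Have the statistician, who already conducts the assignment, keep the main and replacement lists. Release assignments to the therapists, by group or by participant as settled, only after consent, eligibility and baseline CAPS-5 are logged for those concerned, and apply the same to replacements. State that no one who recruits, consents, screens or rates Phase 2 participants has access to any list.
- **Section 6.2.3:** list the unblinded staff by role, consistent with section 3.
- **Sections 4.3, 6.2.1 and 11.2:** name assessor and coordinator as separate roles in the consent text.

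The cost is protocol wording and a message from the statistician at each release, with no added staff. The downside is a small scheduling step before the first session.

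### Phase 2 randomisation is described with two incompatible units, the therapy group and the individual subject, and the planned analysis takes no account of the four therapy groups

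*Combined protocol and SAP*

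**What the plan says.** All of the randomisation detail is in Section 3 (Randomization) of the combined protocol and SAP, and it falls into two parts.

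- **Groups as the unit.** "In Phase 2, groups will be randomized in a 1:1 allocation ratio to CM or Relaxation Training". "Random assignment of groups to study conditions will be conducted by study statistician", and this happens "after the groups have been formed". Section 9.2 (Treatment Assignment Procedures) also says that groups are assigned.
- **Subjects as the unit.** Before enrolment the statistician writes a program to "create a list of subject identification numbers with randomized treatment assignments". "Variable blocked randomization will be used with random block size (4 or 6" closes with the two permitted block sizes. The paragraph ends: "Subjects will be randomized to study treatment group in a 1:1 ratio".

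Section 6.2.2 places randomisation within a month of baseline and within a week of the groups starting. That settles when it happens, not what is randomised.

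On custody, Section 3 says of the list: "which will be held by the unblended project coordinator during the trial" (the adjective is evidently a misprint for unblinded). Section 6.2.3 keeps all personnel blind until data lock, except one named person who carries out the randomisation and the therapists.

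On replacement, Section 3 says: "Separate lists (up to 4) of replacement subject identification numbers will also be created so that replacement subjects are assigned the same treatment" as the person who left. Section 9.3 declares an intention-to-treat analysis of all subjects.

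Section 9.6 makes superiority of compassion meditation over relaxation the primary analysis, by analysis of variance, and reads the effect size against its 95% confidence interval. It lists mixed models only in connection with missing data and drop-out.

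**The concern.** The two parts of Section 3 differ in the unit and in what carries the assignment: a formed group, or a subject number on a list prepared in advance. Staff following one part would not be following the other. Phase 2 is meant to show whether a randomised trial is feasible (Sections 3 and 9.2), so the procedure needs a single reading.

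The unit also governs the inference. If whole groups are assigned, the comparison rests on four units, and a person-level interval is too narrow to carry forward into planning. Separately, members of one therapy group share a therapist, sessions and one another, so their outcomes may be correlated however they were allocated. The plan has no term for this.

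Two smaller matters follow from the same paragraph. The lists of unblinded roles do not match, and replacements take an arm fixed by who left, so they are not independently randomised.

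**Working it through.** **Inputs.** From Section 9.2: four groups, two per arm, 6 to 12 members each, about 40 participants. From Section 3: blocks of 4 or 6. The documents give no ICC, SD, power or alpha. ICC values are therefore assumed, results are in SD units, and tests are two-sided at 5%.

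**The plan's own figure.** 4 × 6 = 24 to 4 × 12 = 48, so about 40 lies in range and corresponds to 4 × 10. There is no power calculation to reproduce. I use 10 per group, 20 per arm.

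**Do the two parts fit together?** Blocks of 4 or 6 are workable for about 40 subjects. They are not a natural device for four groups, and a block of 6 could not be filled by them. So the block sentence belongs to the subject-number list, and the sentences about formed groups belong to a different scheme. A two-stage procedure (people to groups, then groups to arms) would reconcile them, but it is not written and would not explain subject numbers that already carry treatments.

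**If groups are the unit.** The number of ways to choose two of four groups is C(4,2) = 6. The smallest two-sided randomisation p-value is 2/6 = 0.33. A comparison of group means has 4 − 2 = 2 degrees of freedom.

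**Interval half-width for the standardised difference.** Half-width = t × √[(2/20) × (1 + 9 × ICC)], with t = 4.303 on 2 degrees of freedom or 2.024 on 38.

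| Assumed ICC | 38 df | 2 df | Ratio |
|---|---|---|---|
| 0 | 2.024 × 0.316 = 0.64 | 4.303 × 0.316 = 1.36 | 2.13 |
| 0.01 | 0.67 | 1.42 | 2.13 |
| 0.05 | 0.77 | 1.64 | 2.13 |
| 0.10 | 0.88 | 1.88 | 2.13 |

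At equal ICC the ratio is always 4.303/2.024 = 2.13. Other group sizes, at ICC 0: groups of 6 give 0.85 against 1.76; groups of 12 give 0.58 against 1.24.

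**Effect of group delivery on a person-level analysis.** I simulated four groups of 10, two per arm, with no treatment effect and normal group effects, tested by a two-arm analysis that ignores groups. Type I error was about 5%, 6%, 10% to 11% and 16% at ICC 0, 0.01, 0.05 and 0.10. The model contains only groups nested in arm, so the result applies whichever unit was randomised.

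**Roles.** Besides the therapists, Section 3 has two roles that know assignments: the statistician who assigns and the coordinator who holds the list. Section 6.2.3 excepts one person. Unless one person fills both roles, Section 6.2.3 omits one.

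**Replacements.** The arm is inherited from a pre-made slot. No trigger or time limit is stated. Read plainly, Section 9.3 brings both the replaced and the replacing subject into the analysis.

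**The case against.** The best defence is that this is a pilot. Section 9.1 calls it developmental, and Section 9.6 says that effect size is not the main focus and that all analyses are preliminary. That stands and limits the harm. It does not tell staff which scheme to follow, and Section 9.6 places its caution in the confidence interval, which is the quantity affected.

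Several stronger readings are tempting, and the documents do not support them:

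- *The procedure cannot be carried out.* This applies a block of 6 to four groups, a hybrid that Section 3 does not clearly state. Each scheme works alone; the defect is that both are given.
- *The interval is up to 2.9 times too narrow.* That divides 1.88 (ICC 0.10) by 0.64 (ICC 0). At equal ICC the ratio is 2.13.
- *The 16% error rate comes from randomising groups, so randomising subjects cures it.* It comes from delivering treatment in groups and persists under either unit.
- *The blinding sections are proven to conflict.* The name in Section 6.2.3 is removed. An omitted role is probable, not shown.
- *Allocation concealment is broken.* Section 4.3 has an assessor or study coordinator take consent, but nothing identifies that person with the list holder. Nothing separates the roles either. Original members are partly protected because assignment follows group formation and baseline.
- *Replacements bias the comparison.* They inherit a randomised slot. Any bias cannot be derived from the documents.

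**Conclusion.** The point holds as an unresolved unit of randomisation together with an analysis that does not reflect the four therapy groups. The contradiction is plain on the page and needs no assumption. If groups are the unit, the comparison has 6 possible assignments and 2 degrees of freedom, and a half-width of 1.36 SD in place of 0.64 SD; this takes 10 per group and ICC 0. The type I error of about 6% to 16% rests on an assumed ICC of 0.01 to 0.10, is a consequence of group delivery, and is separate from the choice of unit.

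The mismatch of unblinded roles and the replacement rule are minor and less certain. A reader might infer that the randomisation is unworkable or the trial compromised. The documents support neither. This is a repair to the plan that should be made, proportionate to a pilot.

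**What to change.** 1. **State one unit identically in Sections 3 and 9.2.** If the group, remove the subject-number list, the blocks and the closing sentence about randomising subjects. If the subject, keep the blocks and replace the references to randomising groups. The second choice means filling two groups side by side. At Section 9.2's pace of one group per month (stated for Phase 1) that takes about 2 × 1 = 2 months, which must be reconciled with the one-month window in the Précis and Section 6.2.2.
2. **Under either unit, make Section 9.6 reflect the four groups.** Either base the interval on group means (2 degrees of freedom), or label the between-arm contrast descriptive and say that a person-level interval ignores clustering. A random effect for group is a weak alternative, since it is poorly estimated with two groups per arm.
3. **List the same unblinded roles in Sections 3 and 6.2.3**, and have the list held by someone with no consent or assessment role.
4. **Analyse everyone originally randomised as randomised, under Section 9.3.** Either drop the replacement lists and recruit any surplus before randomisation within the stated group size, or keep them and report the comparison with and without replacements.

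The cost is mainly wording. The interval will be wider but honest, and groups may run slightly smaller if replacements are dropped.
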